10.2 INJECTION DOSE AND VISIT COMPLIANCE

Number and percentage of subjects with injection administrated at each visit will be tabulated in the Safety Analysis Set. Cumulative frequency distribution of injections will be summarized.

Dose level frequency distribution (either 100 mg or 300 mg) at each visit will be summarized. Dose level over time during the treatment period for subjects who received 100 mg at the first injection and 300 mg at the first injection will be summarized respectively in the Safety Analysis Set.

Dose modification and its reason (adverse event, lower dose strategy or other) over time will be summarized and its distribution per visit will be plotted using stacked-bar plot. Listing of all subjects who experienced dose adjustments should be provided, including dose prior to and after dose adjustment, and reason for dose adjustment.

Days since last injection will be summarized in the safety analysis set and the distribution of the relative study days of injections will be plotted and listed.

11.0 EXPLORATORY EFFICACY ANALYSES

11.1 URINE DRUG SCREEN (UDS)

The urine sample collected at Screening visit will be tested for drugs listed in the [Table 3](#). The drugs classified as opioids are identified in the same table.

Table 3: Opioid Drug Classification in Urine Drug Screen at Screening Visit.

Drug	Opioid?
Amphetamine	No
Barbiturates	No
Benzodiazepine	No
Benzoylecggonine (Cocaine metabolite)	No
Cannabinoids	No
Opiates	Yes
Codeine	Yes
Hydrocodone	Yes
Hydromorphone	Yes
Methadone	Yes
Morphine	Yes
Oxycodone	Yes
Oxymorphone	Yes
Methamphetamine	No
Phencyclidine	No

At Screening, specific substances were confirmed once the test for Opiates was positive. The UDS for Opioids at Screening will be defined as follows:

The UDS for Opioids is Non-negative at Screening if at least one UDS result (listed in Table) is positive;

The UDS for Opioids is Negative at Screening, if all non-missing UDS results for opioids are negative.

If all UDS measurements for opioids are missing at Screening, the UDS for Opioids will be classified as missing; then be imputed as Non-negative; and be flagged as “Non-Responder Imputation”.

The urine sample collected at visits in the Treatment Period will be tested for drugs listed in the [Table 4](#). The drugs classified as opioids are identified in the same table.

Table 4: Opioid Drug Classification in Urine Drug Screen at visits in the Treatment Period

Drug	Opioid?
Amphetamine	No
Barbiturates	No
Benzodiazepine	No
Benzoylecgone (Cocaine metabolite)	No
Cannabinoids	No
Opiates	Yes
Methadone	Yes
Oxycodone	Yes
Methamphetamine	No
Phencyclidine	No

Different from Screening Visit, specific opiate substances were not confirmed when the Opiates test was positive. Samples were tested for Oxycodone and Methadone separately from the Opiates test.

The UDS for Opioids at visits in the Treatment Period will be defined as follows:

The UDS for Opioids is Non-negative at visits in the Treatment Period if at least one UDS result (listed in Table 4; either the Opiates test, or individual test for Methadone or individual test for Oxycodone) is positive;

The UDS for Opioids is Negative at visits in the Treatment Period, if all non-missing UDS results for opioids are negative.

If all UDS measurements for opioids are missing at visits in the Treatment Period, the UDS for Opioids will be classified as missing; and then be imputed as Non-negative; and be flagged as “Non-Responder Imputation”.

The percentage of UDS Negative for Opioids during the Treatment Period (i.e., only for scheduled visits in the Treatment Period) will be calculated by subject, as the number of visits with UDS Negative for Opioid for that subject divided by the number of scheduled visits during the Treatment Period. Note that this means that subject missing UDS for Opioids for any scheduled visit will be classified as Non-negative for that visit.

The subject-specific percentage of UDS Negative for opioids will be summarized using Descriptive statistics (n, mean (SD), median, min and max). The cumulative distribution function (CDF) will be tabulated for the following categories: $\geq 0\%$, $\geq 10\%$, $\geq 20\%$ through 100%.

A subject is classified as ‘treatment success’, if his/her percentage of UDS Negative for Opioids is $\geq 80\%$ during the Treatment Period. The Number and percentage of treatment successes will be summarized

The number and percentage of subjects with UDS Negative for Opioids by visit at Screening/Baseline or during the Treatment Period will be summarized. The denominator [INDV-6000-301] SAP Version 1.0

of the percentage will be the number of subjects in the Safety Analysis Set. Additionally, the percentage of subjects with UDS Negative for Opioids by visit will also be calculated using the available data approach, where the subjects missing UDS for Opioids for a visit will be excluded from the denominator of the percentage for that visit.

The number and percentage of subjects with positive UDS results will be summarized for the substances tested or for Opiates test during the Treatment Period. The subject will be classified as positive for available substance/Opiates if the UDS result for that substance/Opiates is reported as positive at least once during the Treatment Period. Note that the subjects are only counted once for each substance or for the Opiates test.

All drugs detected in the UDS tests (either Negative or Non-negative) for each subject, for all visits (scheduled or unscheduled), will be listed.

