**Table 2 List of Laboratory Tests**

Hematology:	Serum Chemistry:
Hematocrit	Albumin
Hemoglobin	Alkaline phosphatase (ALP)
Mean corpuscular hemoglobin	Alanine aminotransferase (ALT)
Mean corpuscular hemoglobin concentration	Amylase
Mean corpuscular volume	Aspartate aminotransferase (AST)
Platelet count	Blood urea nitrogen
Red blood cell count	Calcium
White blood cell count with differential	Calculated creatinine clearance c
	Carbon dioxide
	Chloride
Urinalysis:	Creatinine
Appearance	Creatine kinase and subtypes
Bilirubin	Gamma-glutamyl transferase
Color	Globulin
Glucose	Glucose (non-fasting)
Ketones	High-density lipoprotein (HDL)
Leucocyte esterase	Lactate dehydrogenase
Microscopic examination of sediment a	Lipase
Nitrite	Low-density lipoprotein (LDL)
Occult blood	Magnesium
pH	Phosphorus
Protein	Potassium
Specific gravity	Sodium
Urobilinogen	Total bilirubin
	Direct bilirubin
Pregnancy:	Total cholesterol
Urine Pregnancy (only for females not postmenopausal or surgically sterile for at least 1 year)	Total protein
	Triglycerides
	Uric acid
Urine Drug Screen:	
Opioids b	
Cocaine	
Amphetamines	
Methadone	
Cannabinoids	
Barbiturates	
Benzodiazepines	
Methamphetamine	
Phencyclidine	

a Microscopic examination of sediment will be performed only if the results of the urinalysis evaluation are positive (microscopic examination may include but is not limited to WBC count, RBC count, casts, and crystals).

b Oxycodone may not show up in all opiate assays and should be assessed separately.

c Creatinine clearance will be calculated according to the Cockcroft-Gault equation.

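### The SAP's Screening rule for opioid urine status is not limited to opioid tests, so a subject positive only for a non-opioid is both Negative and Non-negative

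*SAP*

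**What the plan says.** SAP 11.1 gives separate rules for Screening and for the Treatment Period.

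- **Screening, Non-negative:** "The UDS for Opioids is Non-negative at Screening if at least one UDS result (listed in Table) is positive". The table meant is Table 3, which has 15 rows: eight marked as opioids (Opiates, Codeine, Hydrocodone, Hydromorphone, Methadone, Morphine, Oxycodone, Oxymorphone) and seven marked as not (Amphetamine, Barbiturates, Benzodiazepine, the cocaine metabolite, Cannabinoids, Methamphetamine, Phencyclidine).
- **Screening, Negative:** "The UDS for Opioids is Negative at Screening, if all non-missing UDS results for opioids are negative".
- **Treatment Period, Non-negative:** a positive result in Table 4, with the qualifying tests spelled out as Opiates, Methadone or Oxycodone. The Negative rule has the same form as at Screening.

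On the order of testing, the SAP says of Screening: "At Screening, specific substances were confirmed once the test for Opiates was positive". Of the Treatment Period it says "Different from Screening Visit, specific opiate substances were not confirmed when the Opiates test was positive", and then "Samples were tested for Oxycodone and Methadone separately from the Opiates test".

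Both statuses feed one table: "The number and percentage of subjects with UDS Negative for Opioids by visit at Screening/Baseline or during the Treatment Period will be summarized" (Table 14.2.1.2). SAP 20.3, on derived efficacy variables, is marked not applicable, so 11.1 is the only place where this status is defined.

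**The concern.** The Screening Non-negative rule lacks the restriction that the Treatment Period rule carries. A subject who used cannabis or cocaine but no opioid satisfies both Screening rules, and the SAP gives no order of precedence. If the Non-negative rule is programmed as written, the Screening row counts any drug use while the later rows count opioid use. There is a single treatment group, so Screening is the only reference row in the table, and part of any apparent change after it would come from the change of definition.

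A second matter is unclear rather than wrong. Both Negative rules use non-missing results only. If oxycodone and methadone were assayed at Screening only after a positive Opiates test, a sample with a negative Opiates test would be called Negative on that one result, whereas on treatment three tests decide.

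**Working it through.** The plan has no figure to reproduce. The 300 in SAP 18.0 is the expected number of subjects, not the result of a power calculation, and is used here only for scale.

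**Step 1: apply the rules to result patterns.**

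| Pattern | Screening, as worded | Treatment Period |
|---|---|---|
| Cannabinoids positive, all opioid rows negative | Non-negative by the first rule, Negative by the second | Negative |
| Opiates positive | Non-negative | Non-negative |
| Oxycodone use only, Opiates test negative, oxycodone assayed | Non-negative | Non-negative |
| Oxycodone use only, Opiates test negative, oxycodone not assayed at Screening | Negative (one non-missing opioid result, and it is negative) | Non-negative (oxycodone is assayed separately) |

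The first line is a contradiction in the stated rules and needs no assumption. The second shows that confirming specific substances after a positive Opiates test cannot alter status, because the subject is already Non-negative. The last two lines differ only in a fact about Screening assays that the SAP does not settle. Methadone-only use with a negative Opiates test follows the same logic.

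**Step 2: size of the rule defect if read literally.** Let k be the share of subjects positive only for non-opioids at Screening. The documents do not give k, so the values are assumed. Subjects relabelled Non-negative = 300 × k.

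- k = 10%: 300 × 0.10 = 30
- k = 30%: 300 × 0.30 = 90
- k = 50%: 300 × 0.50 = 150

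With the Safety Analysis Set as denominator, the Screening negative rate falls by 100 × k percentage points, here 10 to 50.

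**Step 3: size of the conditional assay point.** Let q be the share using only oxycodone or methadone at Screening, and c the share of those whom the Opiates test detects. Both are assumed. If the two assays were run only after a positive Opiates test, subjects wrongly Negative at Screening = 300 × q × (1 − c).

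- c = 0: q of 1%, 2%, 5% and 10% gives 3, 6, 15 and 30 subjects.
- c = 0.5: 1.5, 3, 7.5 and 15.
- c = 1: none.

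If the two assays were run on every Screening sample, the number is zero whatever q and c are.

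**Step 4: direction.** Step 2 lowers the Screening negative rate and Step 3 raises it. If both applied, the net direction could not be known from the documents.

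**The case against.** The best defence is that the missing word is obvious. The variable is the status for opioids, Table 3 exists to classify drugs as opioid or not, and the Negative rule is already limited to opioid results. A programmer would probably supply the restriction, and the contradiction would force the question. That makes the literal outcome less likely. It does not remove the defect: the Treatment Period rule states its restriction in full, and a final SAP should not leave the choice to the programmer.

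A reader might go further and infer that Screening failed to detect oxycodone or methadone use, so that the table sets a blind baseline against sensitive later visits. The documents do not support that:

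- The Screening sentence says that substances were confirmed after a positive Opiates test. It does not say that they were first tested then.
- The contrast drawn with Screening in the Treatment Period text concerns the lack of confirmation. Separate testing of oxycodone and methadone is in the next sentence, and nothing there says it was new.
- The SAP also says "The urine sample collected at Screening visit will be tested for drugs listed in the" Table 3, which has separate rows for both drugs.
- Protocol Table 2 lists methadone apart from opioids and says of the latter: "Oxycodone may not show up in all opiate assays and should be assessed separately". The Schedule of Events repeats this on the urine drug screen row, which covers the Screening column.

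If those directions were followed, there is no assay artefact. What was actually run depends on procedures at the RB-US-13-0003 end-of-study visit, which these documents do not describe. The ambiguity stands; the stronger inference does not.

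It is also fair to say that little hangs on this row. The study's objective is continued treatment and safety monitoring, and no test or change from baseline is planned for this variable. Nor is Screening a pre-treatment baseline, since subjects have just completed a study of the same drug.

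**Conclusion.** The concern holds as a defect in a stated rule. At Screening, a subject positive only for a non-opioid meets both definitions, and the literal Non-negative rule does not match the one used on treatment. Its size in the Screening row is the share positive only for non-opioids, which the documents do not give; 30 to 150 of 300 follows only from an assumed 10% to 50%, and the effect is zero if the intended restriction is programmed.

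The assay question is conditional. It could add 3 to 30 wrongly Negative subjects at Screening if 1% to 10% used only oxycodone or methadone, the Opiates test missed all of them, and the two assays depended on a positive Opiates result. It is zero if any one of those conditions is wholly absent.

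The effect is confined to the Screening row of one exploratory, descriptive table. The per-subject percentage negative, its cumulative distribution and the 80% treatment-success rule use Treatment Period visits only and are untouched.

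**What to change.** 1. In SAP 11.1, reword the Screening rule so that status is Non-negative when *at least one opioid result (marked Yes in Table 3) is positive*.
2. State whether oxycodone and methadone were assayed on the Screening sample regardless of the Opiates result.
   - If they were, define status at every visit, Screening included, from the three common tests: Opiates, Methadone and Oxycodone.
   - If they were run only after a positive Opiates test, footnote the Screening row of Table 14.2.1.2 as not comparable with later visits. Keep the on-treatment results as they are; reducing the comparison to the Opiates test alone would discard valid oxycodone and methadone positives.

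The cost is a few words in the SAP, one check of what was assayed at the RB-US-13-0003 end-of-study visit, and either a common derivation or a footnote. No new samples are needed.

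### In the exploratory urine drug screen analysis, a treatment-visit sample with one or two of the three opioid assays missing and no positive is counted as Negative, unflagged, while a fully missing sample is counted as Non-negative

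*SAP*

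**What the plan says.** SAP 11.1 (Table 4) lists three opioid tests at treatment visits: Opiates, Methadone and Oxycodone. It adds that "Samples were tested for Oxycodone and Methadone separately from the Opiates test". Three rules follow.

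- One positive among the three is enough to make a sample Non-negative.
- The rule for Negative looks only at what was reported: "The UDS for Opioids is Negative at visits in the Treatment Period, if all non-missing UDS results for opioids are negative".
- A sample counts as missing only when none of the three was reported. Such a sample will first be labelled missing "and then be imputed as Non-negative", with a Non-Responder Imputation flag.

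The composite feeds a per-subject percentage: Negative visits divided by scheduled visits in the Treatment Period. A subject is a treatment success at 80% or more. By-visit percentages are produced twice, once over the whole Safety Analysis Set and once on available data, where subjects missing the composite at a visit leave the denominator.

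The protocol's laboratory table (Table 2, footnote b) notes: "Oxycodone may not show up in all opiate assays and should be assessed separately". Note 7 of the Schedule of Events (Protocol Appendix 1) says the same.

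**The concern.** The rules resolve missing data in two directions. With nothing reported, the sample counts against abstinence and is flagged. With one negative methadone result and the other two assays blank, it counts as abstinence and nothing marks it. The documents set no minimum panel, plan no flag for partial panels and plan no sensitivity analysis for them.

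The non-missing wording has a reason at Screening. There, specific opiates were confirmed only after a positive Opiates test, so blanks arise by design. SAP 11.1 says treatment visits differ: there is no confirmation step, and each of the three assays stands alone. A blank among them is genuinely missing information.

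A missing assay can hide a positive but cannot create one, so any misclassification raises the negative rate. The available-data table does not expose this, because a partial panel is not classed as missing and stays in both numerator and denominator.

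**Working it through.** The documents give no figure on this point to reproduce. The check is an enumeration of the rule, the arithmetic of the 80% cut, and an illustration on assumed rates.

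**1. Result patterns.** Each of the three assays can be negative, positive or missing, giving 3 × 3 × 3 = 27 patterns.

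| Pattern | Count | SAP 11.1 | All three required for Negative |
|---|---|---|---|
| Any positive | 19 | Non-negative | Non-negative |
| All three present and negative | 1 | Negative | Negative |
| One missing, two negative | 3 | Negative | Missing |
| Two missing, one negative | 3 | Negative | Missing |
| All three missing | 1 | Missing, imputed Non-negative | Missing, imputed Non-negative |

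Under the SAP, 1 + 3 + 3 = 7 patterns are Negative, and 6 of those 7 are incomplete. Eighteen patterns are partly missing; 12 of them contain a positive and are still Non-negative. Only the remaining 6 are at issue. These are counts of patterns, not of how often each occurs.

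**2. The success threshold.** Protocol Appendix 1 schedules six on-treatment screens: Injections 2 to 6 and EOS/ET. The Day 1 result is the RB-US-13-0003 EOS sample, used for screening. With six visits, 4/6 = 66.7% fails and 5/6 = 83.3% passes, so one partial panel can decide success. If Day 1 were counted as a seventh visit, 5/7 = 71.4% fails and 6/7 = 85.7% passes, with the same consequence.

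**3. Illustration (all rates assumed).** Take six independent visits with true negative probability q = 0.70. Let m be the share of samples that are partial, and h the share of partial, truly positive samples whose positive is hidden by the missing assay. Success is P(X ≥ 5) with X binomial on 6 visits.

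- Truth: 6 × 0.70⁵ × 0.30 + 0.70⁶ = 0.303 + 0.118 = 0.420.
- SAP rule: visit probability q + (1 − q) × m × h.
- All-three rule with partial panels imputed Non-negative: visit probability q × (1 − m).

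| m | SAP rule, h = 1/3 | SAP rule, h = 1 | All-three rule, imputed |
|---|---|---|---|
| 1% | 0.422 | 0.427 | 0.405 |
| 5% | 0.431 | 0.453 | 0.348 |
| 10% | 0.442 | 0.487 | 0.283 |

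The SAP rule errs upward and the imputed alternative errs downward.

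**4. Outputs affected.** In the SAP's list of tables, the composite drives Table 14.2.1.1 (per-subject percentage and its distribution) and Table 14.2.1.2 (by visit), and it also drives treatment success. Table 14.2.1.3 counts subjects positive for each substance from individual assays and does not use the composite.

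**The case against.** The strongest objection is that requiring all three assays can be less accurate. In the illustration at m = 10%, the SAP rule is off by at most 0.487 − 0.420 = 0.067, while the all-three rule with imputation is off by 0.420 − 0.283 = 0.137. If most partial panels without a positive are truly negative, calling them Non-negative misclassifies more samples than it corrects. That arithmetic stands. It shows that non-responder imputation is conservative, which is the convention the SAP already chose for missing samples. It does not justify treating partial panels as complete negatives in the available-data table, where exclusion is the natural handling.

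It is also fair to say that a partial panel carries some information and an empty one carries none. But negative Opiates and Methadone results do not answer the oxycodone question.

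Several stronger readings are tempting and not supported:

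- *Any sample with a missing assay counts as Negative.* No: one available positive makes it Non-negative.
- *Every urine-screen output is affected.* No: Table 14.2.1.3 is not. Results are also listed for all visits (Listing 16.2.30), so partial panels may be traceable there.
- *The documents say none of the three assays can replace another.* The explicit warning concerns oxycodone only. For methadone, the SAP says only that it was tested separately.
- *A definite number of samples is misclassified.* The documents give no partial-panel rate. Even the total of 300 × 6 = 1,800 samples is a ceiling, since subjects may leave at any time (Protocol 3.1). One specimen is tested against one list at each visit, so partial panels may be uncommon.

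**Conclusion.** The point holds, as a minor one. The stated rule can record opioid-negative status that the sample has not established, and it does so unflagged and always in the favourable direction. It affects the per-subject percentage, its cumulative distribution, treatment success and both by-visit percentages.

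The size cannot be determined from the documents. It depends on how often panels are partial and how often the missing assay would have been the only positive. Under the assumptions above, the upward shift in the success proportion runs from 0.002 (1% partial, one third hidden) to 0.067 (10% partial, all hidden). If partial panels are rare it is negligible.

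A reader might infer that this undermines the trial's conclusions. It does not. The study has one treatment group and no comparison (SAP 6.3), its objective is continued treatment and safety monitoring, and SAP 11.0 labels the urine-screen analyses exploratory.

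**What to change.** Amend SAP 11.1 for treatment visits only, leaving Screening as it is:

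- Non-negative if any of Opiates, Methadone or Oxycodone is positive.
- Negative only if all three are available and negative.
- Otherwise missing: imputed Non-negative and flagged in the imputed analysis, and excluded from that visit's denominator in the available-data analysis.

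Report the number of partial panels, and repeat the affected summaries under the current rule as a sensitivity check.

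The cost is a short text change and a small programming change; no new data are needed. The downside is that the imputed analysis becomes more conservative and may understate the negative rate, slightly if partial panels are rare. The count of partial panels and the sensitivity result would show by how much the choice of rule matters.

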20.0 DATA HANDLING CONVENTIONS

20.1 REFERENCE DATES AND ANALYSIS PERIODS

There are two analysis periods in this study:

- Treatment Period (TP)
- Safety Follow-Up Period (SFU).

Treatment Period starts from Treatment Start Date and ends at Treatment End Date. Treatment Start Date (or Day 1) for a subject is the date of the first injection. Treatment End Date for a subject is the maximum of the date of the end-of-study/ Early Termination (EOS/ET) visit and the date of last injection + 28.

Safety Follow-Up Period starts from Safety Follow-Up Start Date and ends at Safety Follow-Up End Date, which are defined for all subject who have assessments in the Follow-Up period.

Safety Follow-Up Start Date for a subject is Treatment End Date +1.

Safety Follow-Up End Date for a subject is defined as the date of visit at Week 29 or unscheduled visit after the Treatment End Date (defined as above) for AE/concomitant medication reporting or lab/vital signs assessment, whichever comes later. That is, Follow-up end date is max (Follow-up Start Date, date of visit at Week 29, last unscheduled visit after the Treatment End Date to report AE/concomitant medication or to do lab/vital signs assessment, if available).

Any records collected prior to first injection date/time will be considered as Screening records. And any records collected after the Treatment End Date will be considered as Safety Follow-up records.

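### SAP 11.1, exploratory urine drug screen: the Screening opioid rule contradicts itself, and the text conflicts on which visits form the denominator of the subject percentage (minor)

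*SAP*

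**What the plan says.** **Screening result.** SAP 11.1, Table 3, lists 15 substances and marks each as opioid or not: 8 are opioids and 7 are not. The rule that follows reads: "The UDS for Opioids is Non-negative at Screening if at least one UDS result (listed in Table) is positive". The next sentence reads: "The UDS for Opioids is Negative at Screening, if all non-missing UDS results for opioids are negative". For visits in the Treatment Period the parallel rule is limited to three tests: "listed in Table 4; either the Opiates test, or individual test for Methadone or individual test for Oxycodone".

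**Subject percentage.** SAP 11.1 defines it as the "number of visits with UDS Negative for Opioid for that subject divided by the number of scheduled visits during the Treatment Period" and adds: "Note that this means that subject missing UDS for Opioids for any scheduled visit will be classified as Non-negative for that visit". A subject at 80% or more is a treatment success. The cumulative distribution is tabulated in categories up to 100%.

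**Treatment Period.** SAP 20.1: "Treatment Start Date (or Day 1) for a subject is the date of the first injection". The Treatment End Date is the "maximum of the date of the end-of-study/ Early Termination (EOS/ET) visit and the date of last injection + 28".

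**Planned samples.** The protocol's Schedule of Events (Appendix 1) marks a urine drug screen at Injections 2 to 6 (Weeks 5, 9, 13, 17, 21) and at EOS/ET (Week 25), and none at Injection 1. SAP 11.1 neither lists nor counts these visits, and SAP 20.3 (derived efficacy variables) is marked not applicable. SAP 20.2 maps an ET sample to the next planned visit that the subject has not completed.

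**The concern.** Two definitions do not give a programmer one answer.

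The Screening rule for Non-negative covers the whole of Table 3, while the rule for Negative looks at opioid results only. A sample positive for cannabinoids and nothing else satisfies both.

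The denominator uses a defined term, the Treatment Period, that ends at a different date for each subject. The note that follows suggests that every planned visit counts, but it does not say whether visits after a subject's own Treatment End Date are included. Protocol 3.1 lets subjects leave at any time, so this is not a rare case. Whether an early leaver with clean samples is a success or a failure depends on which sentence governs. Treatment success is a reported figure in an open-label study, so its rule should be settled before it is programmed.

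**Working it through.** There is no plan figure to reproduce: the SAP never gives the denominator as a number, and the sample size of about 300 has no statistical inputs.

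**1. Screening rule.** Fifteen tests give 2^15 = 32,768 positive/negative patterns. Both definitions are met when all 8 opioid rows are negative and at least one of the 7 others is positive: 2^7 − 1 = 127 patterns. If the Non-negative rule is limited to the 8 opioid rows, no pattern meets both.

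**2. Threshold.** With six visits, 5/6 = 83.3% is a success and 4/6 = 66.7% is not. If Day 1 were counted (seven visits, six samples), the maximum would be 6/7 = 85.7%, so the planned 100% category could not be reached.

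**3. All-negative leaver after j injections, with an ET sample.** There are j − 1 samples at injection visits, plus the ET sample mapped to the next visit, so j negatives. Fixed six: j/6. Own visits: j/j. This assumes the ET visit takes place before a further nominal visit is passed.

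| j | Fixed six | Own visits |
|---|---|---|
| 1 | 16.7% | 100% |
| 2 | 33.3% | 100% |
| 3 | 50.0% | 100% |
| 4 | 66.7% | 100% |
| 5 | 83.3% | 100% |

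The class changes for j = 1 to 4.

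**4. All-negative leaver without an ET sample.** There are j − 1 negatives. If the last injection was on its nominal day, adding 28 days reaches the next nominal visit, which counts as missed. Fixed six, (j − 1)/6: 0, 16.7, 33.3, 50.0, 66.7% for j = 1 to 5. Own visits, (j − 1)/j: 0, 50.0, 66.7, 75.0, 80.0%. On nominal dosing only j = 5 changes class.

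The window is −2/+7 days, however. Injection 2 on Day 29 ends the period on Day 57, so the denominator is 2. Given on Day 27, it ends the period on Day 55, so nominal Day 57 falls outside, the denominator is 1, and the score is 1/1 = 100%. The same happens for any of Injections 2 to 5 given one or two days before its nominal day. The literal denominator therefore also depends on dosing dates.

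**5. Effect on the success rate (illustration).** The documents give no negative rate, within-subject correlation, loss rate or share of leavers with an ET sample, so all four are assumed: 80% negative per visit, the same for leavers and completers; intraclass correlation 0 to 0.7 (beta-binomial; binomial at 0); loss λ of 5 or 10% per urine visit, so 0.95^6 = 73.5% or 0.90^6 = 53.1% reach all six; and none, half or all of the leavers with an ET sample. A leaver with k samples has probability (1 − λ)^k × λ. With x negatives, success on fixed six needs x ≥ 5. On own visits it needs x/k ≥ 0.8 with an ET sample, or x/(k + 1) ≥ 0.8 without one (nominal dosing). Completers score x/6 on both.

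Check at λ = 10%, correlation 0, all with an ET sample. The gap is the sum over k = 1 to 5 of probability × difference in success: 0.0900 × 0.800 + 0.0810 × 0.640 + 0.0729 × 0.512 + 0.0656 × 0.4096 + 0.0590 × (0.7373 − 0.3277) = 0.212, or 21.2 points.

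| Loss per visit | No ET sample | Half | All |
|---|---|---|---|
| 5% | 1.7–2.9 points | 6.9–8.2 | 12.1–13.4 |
| 10% | 2.7–4.6 points | 12.0–14.1 | 21.2–23.6 |

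Example at 10% loss and correlation 0.5: fixed six 41.6%; own visits 45.8, 55.1 or 64.5%.

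**6. Sensitivity.** At 10% loss with all leavers sampled, the gap falls from 21.2–23.6 to 6.0–10.6 points if leavers are 40% negative, and to 2.2–5.0 points if they are 20% negative. In the other direction, if every leaver without an ET sample had a last injection given early, the first column rises to the values in the last.

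**The case against.** The best defence is that a fixed six is the natural reading. The SAP's numerator is tied to the individual subject but its denominator is not. The note scores any missed scheduled visit as Non-negative, missing results are flagged as non-responder imputation, and the main by-visit percentage uses the whole Safety Analysis Set. The SAP is to be read with the protocol, whose schedule gives six urine visits after Day 1. Most of this stands, and it is why the point is a conflict in the text and not a wrong method. It does not close the matter: the note explains a formula restricted to the Treatment Period, and SAP 20.1 gives that term a subject-specific end.

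The Screening slip can fairly be called near-editorial. The variable is labelled as opioid, Table 3 has an opioid column, and the treatment-visit rule is written correctly. The intent is recoverable, but the rule as written is still wrong.

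Four stronger readings are tempting and are not supported:

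- A reader might infer that the SAP adopts a subject-specific denominator and so inflates success. The note points the other way.
- A reader might infer that the Screening slip distorts treatment success. Screening does not enter the subject percentage.
- A reader might take the 100% category as proof of six visits. It argues only against counting Day 1, because own visits can also give 100%.
- A reader might conclude that, without an ET sample, only leavers after five injections are affected. That holds only for dosing on nominal days.

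**Conclusion.** Both points hold and both are minor. The Screening rule is wrong as written and affects only the Screening/Baseline row of the by-visit table. The denominator is a conflict between SAP 11.1 and SAP 20.1.

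The firm result is at subject level: an all-negative leaver with an ET sample after one to four injections is at 16.7 to 66.7% or at 100%, depending on the reading. The effect on the overall success rate is not determined by the documents. The range of about 2 to 24 points rests on 80% negative per visit, 5 to 10% loss per visit and equal negative rates in leavers and completers. Leavers who are less often negative would make it smaller. Protocol 3.3 requires an EOS/ET visit after discontinuation, but Protocol 6.12.3 provides for loss to follow-up, so the figures with every leaver sampled are an upper extreme.

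The by-visit percentages have their own stated denominators and are not touched by the denominator question. The analysis is exploratory and descriptive, with no test, and the safety analyses are unaffected.

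**What to change.** In SAP 11.1:

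- **Screening rule.** Make the result Non-negative if at least one opioid result (Table 3, Opioid = Yes) is positive.
- **Denominator.** State that, in line with the SAP's non-responder approach, the denominator is six for every subject in the Safety Analysis Set (Weeks 5, 9, 13, 17, 21 and 25); that Day 1 is not included; that ET samples are mapped as in Section 20.2; and that any of these visits without a result, including those after early termination, counts as Non-negative.
- **Alternative.** If the sponsor intends a subject-specific denominator, the SAP must say so explicitly and reconcile the non-responder note with it.

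The cost is SAP wording in two places. No new data, table or analysis is needed.
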